9.6. Virtual/Hybrid Visits

Study visits after Day 1 may be conducted via onsite (in person at the study site or specialty lab), offsite (home health visit by study staff or designee), virtual (eg, telephone, video conference), or hybrid (a combination of aforementioned visit types) depending on the nature of the study assessment, technological capability, and acceptability with institutional practices and in alignment with local law and regulatory requirements. These may take place on different days within the study visit window.

Certain assessments and/or procedures will **not** be performed in the home setting (eg, endoscopies, OCT, PFT, cardiac monitoring following treatment initiation or re-initiation, and 12-lead ECG).

Pregnancy testing and central laboratory assessments (eg, blood, stool, and urine samples) can be performed by either onsite visit or offsite visit.

Assessments or procedures that may be conducted virtually, if allowed by local law and regulation, include for example: informed consent process including obtaining written informed consent, medical and medication history to assess eligibility criteria, review of demographic information, social history, AE query, review of concomitant medications, eDiary training, and compliance review/monitoring including study drug administration and questionnaires.

During a virtual assessment, a subject may report an AE that requires a follow-up symptom-focused physical exam or diagnostic test, as determined by the Investigator. In this scenario, the Investigator may have the subject return to the study site for an unscheduled study visit to perform the assessment.

For study drug accountability, the medication bottle and remaining tablets may be visually inspected and counted on video conferencing. Subjects must return the dispensed bottle with the remaining tablets along with any empty bottles to the study site at the next onsite visit. See Section 8 for study treatment management.

Regardless of how a study visit and its associated procedures are conducted, all study procedures should be performed by qualified study site staff or qualified individual as delegated by the Principal Investigator.

Study visits are designated accordingly in the Schedules of Assessments (Table 7 and Table 8).

9.7. Pharmacokinetics

Blood samples for analysis of etrasimod, and if warranted M3 (AR503641) and other metabolite(s) of interest, will be collected at the following timepoints from all subjects who received at least 1 dose of study drug (etrasimod or placebo):

- Pre-dose and at 4 hours (\pm 15 minutes) post-dose (after 12-lead ECG) on Week 0/Day 1
- Pre-dose (trough; within 60 minutes prior to dosing) at Weeks 2, 4, 8, 12, 16, 20, 24, 32, 40, 48, and 52
- At 2-Week and 4-Week Follow-Up visits
- If possible, at the time of any SAE or adverse event leading to study treatment discontinuation

Subjects should be instructed to document the time of their last dose prior to the study visit and the time must be recorded in the eCRF. The time of administration of study treatment during the study visit must also be recorded in the source along with the time of each PK sample.

Blood samples will be processed for collection of plasma fractions for determination of the concentrations of etrasimod, and if warranted M3 (AR503641) and other metabolite(s) of interest. For the placebo group, a selected number of samples will be analyzed.

Plasma PK samples may also be used for profiling of drug-binding proteins, bioanalytical method validation purposes, stability assessments, metabolite assessments, or to assess other actions of etrasimod with plasma constituents.

No urine samples will be collected for PK analysis.

Sample collection, preparation, and shipping will be detailed in a Laboratory Manual.

9.8. Efficacy Assessments

The components of the MMS are used to calculate several of the primary, secondary, [REDACTED] endpoints. The definitions for MMS components are outlined in Section 10.5.

9.8.1. Modified Mayo Score/Mayo Clinic Score

This study utilizes the MMS, which includes the ES, RB, and SF components of the Mayo Clinic score (MCS; Appendix 3) to assess UC disease activity in support of the primary and secondary endpoints. The total score range of the MMS is from 0 to 9, with each component ranging from 0 to 3 (0 = normal, 1 = mild, 2 = moderate, 3 = severe).

The MMS requires daily subject-reported RB and SF scores; therefore, the importance of daily recording of RB and SF by subjects in their daily eDiary should be stressed by the Investigators.

Endoscopy will be used to visualize the mucosa to enable calculation of the ES.

Endoscopic score (ES): The ES reports the worst appearance of the mucosa on flexible sigmoidoscopy or colonoscopy, on a 4-point scale ([Appendix 3](#)). Consistent with regulatory advice, this study excludes friability from the definition of an ES of 1. The ES will be determined by a blinded central reader.

Rectal bleeding (RB): The RB subscore is a subject-reported measure. This item reports the most severe amount of blood passed per rectum in a 24-hour period, on a 4-point scale ([Appendix 3](#)). The subject will record this in their daily eDiary. The method for calculating the RB subscore is described in [Section 9.4.2](#).

Stool frequency (SF): The SF subscore is a subject-reported measure. This item reports the number of stools in a 24-hour period, relative to the normal number of stools for that subject in the same period, on a 4-point scale ([Appendix 3](#)). A stool is defined as a trip to the toilet when the subject has either a bowel movement, passage of blood alone, passage of blood and mucus, or passage of mucus only. The total number of stools passed in a 24-hour period will be recorded by the subject in a daily eDiary. The reference “normal” SF for that subject will be recorded electronically at the Screening Visit and is the number of stools in a 24-hour period when the subject is in remission. If the subject has never achieved remission, the reported SF before initial onset of signs and symptoms of UC will be used as the reference SF. The method for calculating the SF subscore is described in [Section 9.4.2](#).

Physician’s Global Assessment (PGA): The PGA is a physician-reported measure that is a component of the MCS and is used in the calculation of the total Mayo Score. The PGA summarizes the Investigator’s assessment of the subject’s UC disease activity on a 4-point scale ([Appendix 3](#)). The Investigator will record the PGA in the site tablet at the specified study visits ([Table 7](#) and [Table 8](#)). Consistent with regulatory guidance, the PGA will not be used for primary or secondary efficacy assessment in this study.

9.8.1.1. Endoscopy

A flexible proctosigmoidoscopy, performed with a video endoscope following cleansing preparation (oral or rectal cathartic), will be performed during screening (prior to Day 1/randomization), at Week 12, and at Week 52/Early Termination visit. Additional proctosigmoidoscopies may be performed to confirm disease worsening and are required for qualification into the OLE ([Section 5.1.1](#)).

To ensure quality data and standardization, the same endoscopist should be used throughout the study wherever possible. Endoscopy images will be obtained during each endoscopy and will be sent for central reading and determination of the Mayo endoscopic score. A detailed image review charter from the central reading laboratory will outline the endoscopic procedures, video recordings, and equipment. For each subject, a video recording of the entire endoscopic procedure will be performed using an acceptable storage medium. The endoscopic recordings will be read centrally in a blinded manner for mucosal lesions and endoscopic severity by a qualified gastroenterologist according to the image review charter. The ES will be evaluated by the Investigator and the central reader. The central read will be used for determination of efficacy endpoints; however, treatment decisions will be made by the treating Investigator.

Repeated flexible proctosigmoidoscopy may be permitted by the Sponsor when the central reader indicates that the video endoscope data were acquired incorrectly or did not meet the minimal required quality standards.

Note: For subjects with pancolitis > 8 years duration or subjects with left-sided colitis > 12 years without a surveillance colonoscopy within 12 months prior to baseline (Section 4.1, Inclusion Criterion 6), a colonoscopy and biopsies taken in accordance with local standard of care at screening to rule out dysplasia (ie, in place of screening proctosigmoidoscopy) is required. Any adenomatous polyps must be removed prior to their first administration of study treatment.

9.8.1.2. Endoscopic Biopsies

Per inclusion criteria (Section 4.1), a histopathology report supporting the diagnosis of UC must be available in the source documents prior to randomization. Post-randomization detected polyps or suspicious findings during endoscopy will be managed as per local standard of care. If a histopathology report is not available, the screening endoscopy may serve as such with histology evaluated at the local histology laboratory.

Biopsies will be obtained at each endoscopy to support assessment of the histopathology endpoints [REDACTED]. Up to 4 biopsy pairs (ie, total 8) will be collected from the most affected area 15 to 25 cm from the anal verge. For subjects with proctitis only at baseline, biopsies should be taken 8 to 10 cm from the anal verge.

The original location (colonic segment) of biopsy specimens acquired at screening must be clearly indicated. Detailed instructions for endoscopic biopsies (eg, number of biopsies, anatomic site, normal or inflamed mucosa) will be provided.

Biopsy samples will be processed by a central laboratory and histopathologic scoring using the Geboes, Robarts, and Nancy histopathology (Appendix 4) indices will be performed by a blinded central histopathology reader (Geboes 2000, Marchal-Bressenet 2017, Mosli 2017).

Biopsy specimen transfer, processing, slide preparation and digitization of slides for histopathologic scoring procedures will be detailed in a histopathology manual. Histopathology results will not be made available to study sites.

9.8.2. Extraintestinal Manifestations

During the specified full physical examinations (Table 7 and Table 8) specific systems (such as eyes, liver, skin, and joints) will be examined for EIMs for UC.

9.8.3. Additional Health-Related Subject-Reported Outcomes

Subject-reported quality of life instruments will be completed electronically and checked for completeness at the study site as indicated in the Schedules of Assessments (Table 7 and Table 8) and will be used in support of the efficacy outcomes.

Inflammatory Bowel Disease Questionnaire (IBDQ): The IBDQ is a validated 32-item questionnaire used to assess health-related quality of life (HRQoL) in subjects with IBD (UC and CD). Response to each of the questions is graded from 1 to 7 with overall score ranging from 32 (very poor HRQoL) to 224 (perfect HRQoL).

Ulcerative Colitis Patient-Reported Outcomes Signs and Symptoms (UC-PRO/SS): The UC-PRO/SS is used to gather data on the gastrointestinal signs and symptoms of UC directly from the subject. The UC-PRO/SS is a 9-item questionnaire containing 2 domains: bowel movement signs and symptoms (6 items) and abdominal symptoms (3 items). An average score is calculated for each domain; a higher score indicates worse symptoms. The UC-PRO/SS will be administered if and when available.

Medical Outcomes Study 36-Item Short Form Health Survey (SF-36), Version 2 Physical and Mental Component and Domain Scores: The SF-36 is a 36-item, subject-reported survey of subject health. The SF-36 consists of 36 questions measuring 8 health domains: physical functioning, bodily pain, role limitations due to physical problems, role limitations due to emotional problems, general health perceptions, mental health, social function, and vitality. The subject's responses are solicited using Likert scales that vary in length, with 3 to 6 response options per item. The SF-36 will be scored using 2 overall summary scores: physical component summary and mental component summary scores.

Work Productivity and Activity Impairment Questionnaire – Ulcerative Colitis (WPAI-UC): The WPAI-UC consists of 6 questions asking about the effect of UC on the subject's ability to work and perform regular activities.

Urgency Numeric Rating Scale (NRS): The urgency NRS is a single item that measures the severity for the urgency (sudden or immediate need) to have a bowel movement in the past 24 hours using an 11-point NRS ranging from 0 (no urgency) to 10 (worst possible urgency).

Abdominal Pain NRS: The abdominal pain NRS is a single item that measures the “worst abdominal pain in the past 24 hours” using an 11-point NRS ranging from 0 (no pain) to 10 (pain as bad as can imagine).

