- Symptomatic remission: SF subscore = 0 (or = 1 with a ≥ 1 -point decrease from baseline) and RB subscore = 0

Primary efficacy endpoints:

- The proportion of subjects achieving clinical remission at Week 12
- The proportion of subjects achieving clinical remission at Week 52

Key secondary efficacy endpoints:

- The proportion of subjects achieving endoscopic improvement at Week 52
- The proportion of subjects achieving endoscopic improvement at Week 12
- The proportion of subjects achieving symptomatic remission at Week 52
- The proportion of subjects achieving symptomatic remission at Week 12
- The proportion of subjects in clinical remission at Week 52 and who had not been receiving corticosteroids for ≥ 12 weeks prior to Week 52
- The proportion of subjects with mucosal healing at Week 52
- The proportion of subjects with mucosal healing at Week 12
- The proportion of subjects achieving clinical remission at both Weeks 12 and 52

Pharmacokinetic assessments:

Plasma concentrations of etrasimod, and if warranted M3 (AR503641) and other metabolite(s) of interest, will be assessed from samples collected pre-dose and 4 hours post-dose (after 12-lead ECG) on Week 0/Day 1, and pre-dose (trough) at Weeks 2, 4, 8, 12, 16, 20, 24, 32, 40, 48, 52, and at the 2-Week and 4-Week Follow-Up visits. A PK sample should also be drawn, if possible, at the time of any SAE or adverse event leading to study treatment discontinuation.

Plasma PK samples may also be used for profiling of drug binding proteins, bioanalytical method validation purposes, stability assessments, metabolite assessments, or to assess other actions of etrasimod with plasma constituents.

Other assessments:

Biomarker endpoints:

- Change from baseline in level of fecal calprotectin at Weeks 2, 4, 8, 12, 24, and 52
- Change from baseline in level of high-sensitivity C-reactive protein at Weeks 2, 4, 8, 12, 16, 20, 24, 32, 40, 48, and 52
- Change and percentage change from baseline in lymphocyte counts at Weeks 2, 4, 8, 12, 16, 20, 24, 32, 40, 48, and 52

Health-related quality of life endpoints:

- Scores and change from baseline at Weeks 12 and 52 in the following:
 - Inflammatory Bowel Disease Questionnaire total score (IBDQ)
 - Ulcerative Colitis Patient-Reported Outcomes Signs and Symptoms (UC-PRO/SS)
 - Medical Outcomes Study 36-Item Short Form Health Survey, version 2 physical and mental component and domain scores (SF-36)

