9.4.2. Treatment Period

After randomization, the 12-Week Treatment Period of the study will begin (Table 7). A study visit window of \pm 3 days is permitted at each visit beginning with Week 2/Day 15 (PFT and OCT assessments have a window of \pm 7 days). For the Week 12 through Week 48 Visits, and ET Visit, a study visit window of \pm 7 days is permitted. For the Week 52 Visit, a study visit window of \pm 14 days is permitted. Study visits should be scheduled for the morning.

The subscores for SF and RB are derived from the subject eDiary entries. On visits when MMS is calculated, these subscores are derived using the scores from the 3 most recent consecutive days within the 7 days prior to the day of bowel preparation (excluding the day of bowel preparation), averaged and rounded to the nearest integer. If 3 consecutive days are not available, then the average of the 2 most recent consecutive days within the 7 days will be used.

On visits without endoscopy, the SF and RB subscores are derived using the scores from the 3 most recent consecutive days within the 7 days prior to the date of visit, averaged and rounded

to the nearest integer. If 3 consecutive days are not available, then the average of the 2 most recent consecutive days within the 7 days will be used.

It is recommended that procedures are performed in a consistent order and at approximately the same time of day for each visit. Below is the recommended sequence of events:

- Questionnaire administration
- Adverse event review
- Vital signs
- 12-lead ECG (as indicated in the Schedules of Assessments, [Table 7](#) and [Table 8](#))
- Physical examination
- EIMs (as indicated in the Schedules of Assessments, [Table 7](#) and [Table 8](#))
- PFT (as indicated in the Schedules of Assessments, [Table 7](#) and [Table 8](#))
- OCT (as indicated in the Schedules of Assessments, [Table 7](#) and [Table 8](#))
- Blood sample collection for laboratory tests and pre-dose PK sampling

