16. APPENDICES

APPENDIX 1: SCHEDULES OF ASSESSMENTS

Table 7: Schedule of Assessments – Screening and 12-Week Treatment Period

| Evaluation | Screening Period | 12-Week Treatment Period | | | | | 2-Week Follow-Up Visit ^b ± 3 Days | 4-Week Follow-Up Visit ^b ± 3 Days |
|---------------------------------------------------------------------|------------------|--------------------------|--------------------|--------------------|--------------------|------------------------------------------------------|-------------------------------------------------|-------------------------------------------------|
| | -28 to -1 | W0/D1 | W2/D15 ± 3 Days | W4/D29 ± 3 Days | W8/D57 ± 3 Days | W12/D85 / Early Termination ^a ± 3 Days | | |
| Informed consent | X | | | | | | | |
| Inclusion/exclusion criteria | X | X | | | | | | |
| Demographics | X | | | | | | | |
| Medical and social history ^c | X | | | | | | | |
| Ulcerative colitis history | X | | | | | | | |
| Chest X-ray ^d | X | | | | | | | |
| Tuberculosis test ^e | X | | | | | | | |
| Tuberculosis questionnaire ^e | X | X | X | X | X | X | X | X |
| Virology screen (HIV, HBV, HCV) ^f | X | | | | | | | |
| Randomization | | X | | | | | | |
| eDiary instruction ^g | X | | | | | | | |
| eDiary review | | X | X | X | X | X | | |
| MMS ^h | | X | | | | X | | |
| Stool frequency and rectal bleeding subscore ⁱ | | X | X | X | X | X | | |
| PGA for total Mayo Clinic Score | | X | | | | X | | |
| IBDQ, UC-PRO/SS, SF-36, WPAI-UC, and abdominal pain and urgency NRS | | X | | | | X | | |
| Adverse event assessment | X | X | X | X | X | X | X | X |
| Vital signs ^j | X ^j | X ^{i,k} | X | X | X | X | X | X |

| Evaluation | Screening Period | 12-Week Treatment Period | | | | | 2-Week Follow-Up Visit ^b ± 3 Days | 4-Week Follow-Up Visit ^b ± 3 Days |
|------------------------------------------------------------------|------------------|--------------------------|--------------------|--------------------|--------------------|------------------------------------------------------|-------------------------------------------------|-------------------------------------------------|
| | -28 to -1 | W0/D1 | W2/D15 ± 3 Days | W4/D29 ± 3 Days | W8/D57 ± 3 Days | W12/D85 / Early Termination ^a ± 3 Days | | |
| 12-lead ECG ^l | X ^l | X ^{l,m} | | | | X | | |
| Physical examination ⁿ | X | X | X | X | X | X | X | X |
| Extraintestinal manifestations ^o | X | | | | | X | X | X |
| Pulmonary function test ^p | X ^q | | | | | X ^q | X ^q | |

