17.1.4. Urgency Numeric Rating Scale

The urgency NRS is a single item that measures the severity for the urgency (sudden or immediate need) to have a bowel movement in the past 24 hours using an 11-point NRS ranging from 0 (no urgency) to 10 (worst possible urgency).

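### The urgency and abdominal pain scales look back 24 hours at the endoscopy visits, and no rule found keeps bowel preparation out of that recall

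*Protocol*

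**What the plan says.** Protocol 9.8.3 defines an 11-point urgency scale that "measures the severity for the urgency (sudden or immediate need) to have a bowel movement in the past 24 hours" and an abdominal pain scale for the "worst abdominal pain in the past 24 hours". SAP 17.1.4 and 17.1.5 repeat both recall periods. The endpoints in the protocol synopsis are "Scores and change from baseline at Weeks 12 and 52 in the following" list of instruments, which includes both scales.

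In Table 7 the row "IBDQ, UC-PRO/SS, SF-36, WPAI-UC, and abdominal pain and urgency NRS" is marked at Day 1 and Week 12/early termination only. In Table 8 the corresponding row is marked at Week 52/early termination only. Protocol 9.8.1.1 places endoscopy, after an oral or rectal cathartic, at screening, Week 12 and Week 52/early termination.

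For stool frequency and rectal bleeding, Protocol 9.4.2 takes diary days before preparation, "excluding the day of bowel preparation". Protocol 9.6 allows the assessments of one visit to fall on different days within the window. Among the tasks that may be done virtually it lists "compliance review/monitoring including study drug administration and questionnaires".

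**The concern.** A cathartic causes urgency and cramping directly. If preparation falls inside the 24-hour recall, the rating reflects the procedure as well as the colitis. The Day 1 rating is normally free of this, so the change from Baseline compares an unprepared rating with a possibly prepared one. The protocol already protects the sibling symptoms, stool frequency and rectal bleeding, against this problem. At stake is how well two patient-reported outcomes, collected to support the efficacy results, measure disease symptoms.

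**Working it through.** **1. Timing.** Inputs: Protocol 9.3.11, 9.8.1.1, Tables 7 and 8.

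| Visit | Scales rated | Endoscopy | Can the 24-hour recall include preparation? |
|---|---|---|---|
| Screening | No | Yes | No rating |
| Day 1 | Yes | No; the screening endoscopy comes first, and its central read takes about 5 to 12 days | Normally not |
| Week 12/early termination | Yes | Yes | Possible |
| Weeks 16 to 48 | No | Not scheduled | No rating |
| Week 52/early termination | Yes | Yes | Possible |

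Some early termination visits have no endoscopy (for example, when one was done within the previous 4 weeks), so those ratings may be clean. Table 8 footnote c removes the preparation day from the diary days leading up to the Week 52 visit, so preparation is expected close to that visit.

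**2. Search for a rule.** I found no preparation exclusion, and no instruction to rate before preparation, for these scales in Protocol 9.8.3, in Tables 7 and 8 and their footnotes, or in SAP 6.2, 6.4, 17.1.4 or 17.1.5. The advice in Protocol 9.4.2 to give questionnaires first helps only if preparation is given later that day, because the item looks back 24 hours.

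**3. Direction.** Suppose two subjects both rate 6 at Day 1, and their true Week 12 urgency is 1 and 4. Let preparation urgency be 3 and the reported score be the higher of the two. The first subject reports 3, a change of 3 − 6 = −3 instead of 1 − 6 = −5. The second still reports 4, a change of −2. The gap between them shrinks from −3 to −1. Preparation masks more in the quieter subject, so it dilutes the comparison if etrasimod works. If preparation instead added the same amount to every rating, the change from Baseline would still be understated, but the between-arm difference would be preserved except near the ceiling of 10.

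**4. Size.** The documents give no expected score, spread or power for these scales, so there is no stated figure to reproduce and every input here is assumed. Baseline mean 6 (SD 2); true post-baseline means 3.0 for etrasimod and 4.5 for placebo (SD 2.5); preparation ratings SD 2; all ratings rounded and bounded at 0 and 10. A share q of ratings overlaps preparation. Two reporting rules are used for those ratings: the higher of the true and preparation ratings, or the midpoint of the true rating and that higher value. Difference = etrasimod mean − placebo mean; loss = 1 − (difference ÷ −1.39), where −1.39 is the simulated difference at q = 0.

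| Reporting rule | Preparation mean | q | Difference | Loss |
|---|---|---|---|---|
| Higher rating | 2 to 3 | 25% | −1.30 to −1.25 | 6 to 10% |
| Higher rating | 2 to 3 | 50% | −1.21 to −1.13 | 13 to 19% |
| Midpoint | 6 | 50% | −1.13 | 19% |
| Higher rating | 4 | 50% | −1.04 | 25% |
| Higher rating | 6 | 25% | −1.14 | 18% |
| Higher rating | 6 | 50% | −0.88 | 37% |
| Higher rating | 8 | 50% | −0.76 | 45% |
| Higher rating | 6 | 100% | −0.35 | 75% |

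Repeat runs agree to about 0.02. With the higher-rating rule, preparation mean 6 and q = 50%, the etrasimod change from Baseline is about −1.3 instead of −2.85.

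**The case against.** The strongest reply is that overlap is inferred. The recommended order of procedures in Protocol 9.4.2 does not list endoscopy, so it does not put questionnaires and endoscopy on one day. Protocol 9.6 lets them fall on different days and lets questionnaires be done virtually. A rectal preparation given on site after the questionnaires leaves the rating clean. This stands: overlap is permitted and plausible, not certain, and a reader who infers that every Week 12 and Week 52 rating is contaminated goes beyond the documents.

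Second, the size depends on the reporting rule. Only the pain item asks for the worst value; the urgency item ("to have a bowel movement in the past 24 hours using an 11-point NRS") does not. A reader might take a loss of 25 to 45% as the expected effect, but that range needs the higher-rating rule, preparation means of 4 to 8 and half of ratings overlapping. Nothing in the documents fixes any of these.

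Third, the text available to me lacks most of Protocol 10.9.1 and the opening of SAP 17. A rule there cannot be excluded.

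Fourth, the endpoints are supportive. Protocol 10.12.1 gives endpoints outside the primary and key secondary set nominal p-values without multiplicity adjustment. This stands too, and it limits the weight of the point. It does not remove the point, because preventing the overlap costs almost nothing.

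**Conclusion.** The point holds in limited form. The plan as available allows both scales to be rated with bowel preparation inside the recall after baseline but normally not at Day 1, and no rule was found that prevents or identifies this. Where it happens, improvement from Baseline is likely understated in both arms. The treatment difference is likely diluted, provided preparation masks low scores more than high ones. The loss may be zero, roughly 6 to 20% under mild assumptions at 25 to 50% overlap, or larger under stronger ones. These figures are illustrations, not estimates for this trial.

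Two further inferences are not supported. The coprimary endpoints and symptomatic remission are not exposed, because stool frequency and rectal bleeding already exclude the preparation day. Nor is there a reason to expect bias in favour of etrasimod: preparation applies to both arms, and the likely effect is dilution.

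**What to change.** **Protocol 9.8.3 and the footnotes to Tables 7 and 8:** require the urgency and abdominal pain scales for Weeks 12 and 52 to be completed before bowel preparation starts, remotely if needed, as Section 9.6 allows.

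**SAP 17.1.4 and 17.1.5:** flag ratings whose 24-hour recall overlaps preparation and add a sensitivity analysis that excludes them. The preparation day is already needed to derive stool frequency and rectal bleeding, so a date-based flag (rated on the preparation day or the day after) should be feasible. For ratings already collected, only this part can help.

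I would not drop flagged ratings from the main analysis. Each scale has only two scheduled post-baseline time points, and SAP 17.2 imputes nothing, so exclusion could remove much of the data if overlap is common.

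**Cost:** some subjects rate a day or more before the visit, and there is a little extra analysis work.
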